### 3. Study Design

This study is a randomized placebo-controlled clinical trial. Investigators will be blinded to the type of stimulation given (sham versus active) through use of a computer-assisted pre-programmed tDCS stimulator. Subjects will be blinded to sham versus active through the use of low-current (up to 0.2 mA) sham stimulation, which provides a tactile sensation similar to active 2.0 mA stimulation. Ramping up and down the current at the beginning of stimulation also prevents subjects from distinguishing sham from active. The duration of an individual subject's participation in the research may range up to 1 year. The duration anticipated to enroll all subjects is 3 to 4 years. The expected duration for the investigators to complete the study (complete analysis) is 5 years.

**PROTOCOL TITLE:** Transcranial direct current stimulation for treatment of deficits after traumatic brain injury.

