#### 4. Study Timelines

GOAL	YEAR 1	YEAR 2	YEAR 3	YEAR 4	YEAR 5
Project Progress	Human Subjects Review Board approval completed  Equipment purchased  Biostatistical training completed  Clinical Supervisor and Research Assistant training completed  Begin participant recruitment (targeted enrollment of 10 active tDCS patients and 10 controls)  Progress reported to Human Research Protections Office (HRPO), PI, and NIH.	Recruited 20 active tDCS patients and 20 controls  Preliminary data analyses on tDCS effects completed, in preparation for NIH grant submission  Progress reports submitted to to HRPO, PI and NIH	Recruited 10 active tDCS patients and 10 controls  Completed preliminary data analyses of group differences in tDCS effects across groups  Progress reports submitted to to HRPO, PI and NIH	Progress reports submitted to to HRPO, PI and NIH  Complete all data analysis	Progress reports submitted to to HRPO, PI and NIH  Closure Report submitted to HRPO

PROTOCOL TITLE: Transcranial direct current stimulation for treatment of deficits after traumatic brain injury.

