Randomization will occur at time of consenting. The study coordinator who consented the patient will use a coin-tossing procedure to determine whether the subject is assigned to the active group (group 1) or control group (group 2). Modifications will be made as necessary toward the end of enrollment to ensure equal group size and balanced distribution of demographic variables such as age and gender. The study coordinator will not be blinded to group assignment, and with the assistance of the Clinical Core, will program the TDCS devices to deliver active or sham stimulation depending on which group the subject has been assigned. However, the coordinator will not be involved in performing any stimulation procedures. The study technician and principle investigator, who will be responsible for administering the stimulation, will not be aware of which group receives active versus control, and will thus be blinded, as the TDCS device will only display the group number (1 or 2).

Once group membership is determined, individual participants may undergo demographic data collection, neuropsychological assessments and tDCS treatment sessions. They may also undergo EEG and/or MRI. Direct identifiers of participants will be maintained on a separate database that will be stored behind locked doors, in a locked filing cabinet in a secure area of the Clinical Core.

**Demographic Data:** As part of the initial assessment, basic demographic data regarding the subject may be noted down, including age, gender, socioeconomic status, educational attainment, handedness, use of common stimulants such as caffeine, and brain injury severity. They may also be asked if they are willing to allow their medical record to be accessed, for the purposes of confirming details about any TBI as well as obtaining results of neuroimaging studies done at the time of injury or afterward. This will include medical, surgical, neurological and psychiatric history, results of lab tests, brain scans, electroencephalography tests, medication lists, information from doctor's visits and hospital visits.

**Neuropsychological testing procedures:** All neuropsychological testing will be administered in the Center for Brain Recovery and Repair Core by trained study personnel under direct supervision of core directors, clinical neuropsychologists Drs. [name], [name], or the PI. The primary dependent outcome variables to be studied are the three composite scores generated by

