Statistical analyses will utilize the CTSC Biostatistics core. Power analyses and statistical analysis strategy were determined with our statistician [name], who will continue to provide recommendations and support throughout the project. Sufficient group sizes were determined on the basis of data derived from preliminary studies. Clark and colleagues found an effect size of Cohen's  $d = 1.2$  for tDCS to induce improvements in cognition. For our power calculations we will assume a more conservative effect size of  $d = 0.7$  which is consistent with a recent meta-analysis of tDCS effect sizes. With 40 tDCS treatment patients compared to 40 sham patients and an effect size of 0.7, we have 80% power to detect effects of active versus sham treatment in a two-sample t-test. Power in the linear mixed model analysis should be superior that that of the t-test. For Aim 1.1, the central analyses evaluate group (active vs. sham) differences in the EEG data and on the three Examiner composite variables across the three initial time points (before, immediately after, and 1 month after tDCS stimulation protocol). To test this hypothesis, three separate linear mixed models analyses will be performed using the three Examiner composite scores (Fluency, Cognitive Control, Working Memory) as dependent variables. In each analysis, we will incorporate three covariates that may predict variation in learning (severity: mild vs. moderate, premorbid intelligence: WTAR score, and symptom burden: NSI). This will allow us to determine predictors of treatment response (Specific Aim 1.3). Sex, ethnicity, and age will also be entered into the statistical model. The effects of these covariates will be estimated by constructing appropriate contrasts in model effects. A similar set of analyses will evaluate group differences on the variables assessed in our long-term oral/phone follow-up (five data points: (1) before tDCS, (2) immediately after tDCS, (3) 1 month post-tDCS, (4) 6 months, and (5) 1 year) for Aim 1.2. For these analyses dependent variables will be the total cognitive items score of the NSI and the PROMIS-29 profile total score). Significant effects will be followed up with more fine-grained analysis of the components of composite scores. The use of linear mixed-models minimizes the adverse impact of a missing data point, which may well occur in a longitudinal clinical study such as this. Expected attrition will be taken into account with an intention-to-treat analysis. Missing data patterns will be analyzed to assess the extent to which they are informative (in contrast to missing at random), and analyses adjusted accordingly. All EEG data will undergo standard preprocessing (e.g. motion correction, spatial normalization) and quality control prior to statistical modeling. Depending on the specific question of the study, data may be analyzed using the general linear model, independent components analysis, machine learning techniques, or a variety of other standard approaches for neuroimaging data.

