
## 12. Provisions to Monitor the Data to Ensure the Safety of Subjects

Data safety and monitoring will be carried out to ensure and maintain the scientific integrity of this project and to protect the safety of our participants. Safety monitoring is the process during the study that involves review of accumulated outcome data for groups of subjects to determine if any of the procedures practiced should be altered or stopped. Ultimately, the PI ([name]) will be responsible for monitoring the safety of the study and complying with the reporting requirements. An independent Data Safety and Monitoring Board (DSMB) will review the study data on a quarterly basis with the PI to ensure participant safety. The DSMB for this study will be composed of [name], the medical director of the Electroconvulsive Therapy Service at UNM, and [name], staff epileptologist of the Epilepsy Monitoring Unit at UNM. Their experience in assuring safety of brain stimulation therapies and seizure monitoring protocols make them ideally suited to serving on this project's DSMB. Continuous, close monitoring of participant safety will include prompt and frequent reporting of safety data (i.e., adverse/serious adverse events) to the

**PROTOCOL TITLE:** Transcranial direct current stimulation for treatment of deficits after traumatic brain injury.

DMSB, the University of New Mexico Health Sciences Center Institutional Review Board (UNMHSC IRB) and/or appropriate NIH staff with oversight responsibility. The PI will provide a summary of the safe conduct of the study to NIH on an annual basis as part of the progress report. All AEs occurring during the course of the study will be collected, documented, and reported to the UNMHSC IRB.

The review of data may result in early termination of the study, amendment to the protocol, or changes to the data collection plan or study forms if it appears that there are adverse events occurring at a rate significantly greater than that found in similar tDCS studies involving subjects with neurological disorders (ie. stroke). Should the protocol or data collection plans or study forms be amended as a result of data review, the IRB will be notified and the amendment approved prior to study amendment implementation. In addition, the participants will be notified of any significant new findings that develop during the course of research that may affect their wish to continue participation in the study.

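### No rule keeps by-arm results from the blinded PI and technician, although tDCS effects are analysed from Year 2 and the PI attends quarterly reviews of outcome data

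*Combined protocol and SAP*

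**What the plan says.** **Early analyses.** The Year 2 column of Section 4 lists "Preliminary data analyses on tDCS effects completed, in preparation for NIH grant submission". The Year 3 column lists "Completed preliminary data analyses of group differences in tDCS effects across groups". Completion of all analysis is placed in Year 4. Section 3 adds: "The duration anticipated to enroll all subjects is 3 to 4 years".

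**Quarterly reviews.** Section 12 defines safety monitoring as "review of accumulated outcome data for groups of subjects to determine if any of the procedures practiced should be altered or stopped", and has the Data Safety and Monitoring Board meet quarterly with the PI. Section 16 (tDCS risks) repeats that the PI and the Board go over outcome data each quarter. Section 31 describes the same quarterly review as one for side effects or adverse events.

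**Blinding.** Section 3 requires the investigators to be blind to stimulation type. Section 10 says that the technician and PI who administer stimulation "will not be aware of which group receives active versus control, and will thus be blinded", because the device shows only a group number. The same paragraph, repeated in Section 18, states that group 1 is active and group 2 is control.

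**Not found.** The documents give no alpha level, interim boundary or closed session. They do not say whether the preliminary analyses are blind to arm, and they set no rule on who may see results by group. Section 11 places the statistical work with the CTSC Biostatistics core but does not restrict where the results go.

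**The concern.** The PI is close to the outcomes. Besides giving stimulation, the PI may supervise neuropsychological testing (Section 10), is among those who collect data, and reviews data for quality control (Section 14). If the PI or technician learns which arm is ahead while patients are still being treated and tested, that knowledge can affect how sessions are run and how outcomes are obtained. The risk is greatest for the interview-based depression and symptom measures. The double blind exists to prevent this, and the text as written leaves a route around it.

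The second, conditional, issue is error control. If an early active-versus-sham result could be reported as a finding, or could change the conduct of the trial, the final test would no longer hold its nominal level.

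**Working it through.** **1. The plan's own figure.** The plan gives no number for interim looks. Its nearest figure is in Section 11: "With 40 tDCS treatment patients compared to 40 sham patients and an effect size of 0.7, we have 80% power to detect effects". A two-sample t-test with 40 per arm and d = 0.7 has 87.1% power at two-sided 0.05. The stated 80% is matched at two-sided 0.025 (79.9%) or with 33 per arm at 0.05 (80.0%), and neither condition is stated. That gap is a separate matter. Here the sentence supplies only the planned 40 + 40, and the mismatch shows that alpha must be assumed. I use two-sided 0.05.

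**2. Information at the Year 2 look.** Section 4 plans 10 + 10 in Year 1, 20 + 20 in Year 2 and 10 + 10 in Year 3.
- Recruited by the end of Year 2: 10 + 20 = 30 per group.
- Fraction: 30 / 40 = 0.75.

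This is an upper bound, because it counts recruits and not completed post-stimulation or 1-month visits.

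**3. Position of the Year 3 look.** On the table's counts, recruitment reaches 40 + 40 in Year 3, so this analysis may fall at full enrolment. It precedes full accrual if enrolment takes the 4 years that Section 3 allows. Year 2 is the clear interim look.

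**4. Access, statements side by side.**
- The PI must not know which group is active (Sections 3 and 10).
- The PI sits in quarterly reviews of outcome data (Sections 12 and 16).
- Section 12 defines the monitoring material as data for groups of subjects.
- The meaning of groups 1 and 2 is printed in Sections 10 and 18.

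A table by group number shown at such a review would be unblinding to anyone who has read the protocol. Only Section 31's narrower description points away from this, and it conflicts with Section 16.

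**5. Type I error if a look could count.** Take one unadjusted two-sided 0.05 test at fraction 0.75 and one at the end.
- Correlation of the two statistics: sqrt(0.75) = 0.866.
- P(|Z1| > 1.96 or |Z2| > 1.96) = 0.0732.
- Excess over the nominal level: 7.3% − 5.0% = 2.3 percentage points.

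Sensitivity to assumed timing, each with the final test:

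| Looks before the final test | Type I error |
|---|---|
| 75% | 7.3% |
| 50% | 8.3% |
| 75% and 95% | 8.0% |
| 50% and 90% | 9.4% |

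These figures apply to one composite. Section 11 says that "three separate linear mixed models analyses will be performed using the three Examiner composite scores"; multiplicity over the three is a separate question.

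**The case against.** The strongest reply is that nothing here is an efficacy interim analysis. The plan contains no efficacy or futility stop and no early claim. The only stated trigger for termination or amendment is an excess of adverse events (Section 12), and amendments need IRB approval first. The Year 2 analysis has a declared purpose, the grant submission. A look that cannot end the trial or support a claim does not inflate the final test. This stands, and it is why the error-rate point can only be conditional.

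Three stronger readings are tempting, and the documents do not support them.
- **Each quarterly review is an efficacy test.** A reader might infer this from the references to outcome data and then compute a much larger error rate over many looks. The purpose given in Sections 12 and 31 is safety, and no efficacy test is attached to any review.
- **The PI is shown results by arm.** No section says so. It is an inference, although a strong one given step 4. Nothing says that the technician attends the reviews.
- **Active versus sham is certainly what is analysed in Years 2 and 3.** Section 4 speaks of tDCS effects and of groups, and its controls could be sham patients or healthy controls, since 80 healthy controls are also planned (Sections 6 and 10). Sham is the likelier reading because 40 + 40 matches the power calculation.

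The reply does not answer the access problem. A safety purpose does not require a blinded PI to see outcome data, and use of the Biostatistics core is not a firewall unless the plan says who receives its results.

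**Conclusion.** The point holds as a gap in blinding and access. The plan requires the PI and technician to be blind. It also has the PI review outcome data quarterly, schedules an analysis of tDCS effects with at most 75% of the 40 + 40 recruited, and prints the group key. Followed as written, it permits exposure of blinded staff to arm trends and makes it likely, without stating that it occurs. Sections 12 and 16 also conflict with Section 31 on what the quarterly review covers.

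The effect on type I error is conditional and modest: about 7.3% instead of 5% for one Year 2 look plus the final test. That assumes two-sided 0.05, a full 75% of information, and a look that could support a claim or change conduct. If the look can do neither, the final test keeps its level and only the blinding concern remains. The size of any bias from unblinding cannot be calculated from the documents.

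**What to change.** 1. **Sections 12, 16 and 31.** Reconcile the descriptions of the quarterly review. Limit reviews that the PI attends to safety data pooled over arms. Any by-arm data are seen only by the Board, in closed session.
2. **Section 4.** State that analyses before the last 1-month visit are blind to arm. If by-arm results are needed, state that the CTSC statistician holds them, that they are kept from the PI, technician and assessors, and that they have no effect on conduct or conclusions. Add that active-versus-sham efficacy is tested once, at the end.
3. **Sections 10 and 18.** Use group codes whose meaning is not printed in the protocol.

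The cost is a few sentences and a separately held code list. The real downside is that the grant submission would rely mainly on pooled preliminary data, such as recruitment, variability and pre-post correlation, which is less persuasive than a by-arm comparison.

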## 5. Study Endpoints

Primary endpoint: change in scores on the EXAMINER battery from before to after stimulation.

Secondary endpoints: change in score on the Neurobehavioral Symptom Inventory, Beck Depression Inventory-II, Hamilton Rating Scale for Depression, change in frontal midline theta synchrony on EEG, change in MRI abnormalities, and quality of life measure from time 0 to 1 year.

## 6. Research Setting

All testing, analytical, and research activities will take place at the Clinical Core, UNM Center for Brain Injury Recovery and Repair, located in Domenici Hall, MIND Research Network.

Subjects will be identified and recruited from the UNM ED and other local EDs via the CTSC patient recruitment service, as well as coordination with ED providers and posted advertisements. Healthy controls will be recruited through online advertisements, word of mouth and flyers. As the only Level 1 trauma center for the state of New Mexico and the community hospital for Bernalillo County and the city of Albuquerque, which is the most populous city in the state, UNM treats the majority of TBIs presenting in the state. Approximately 10,000 New Mexicans receive treatment for a TBI in hospitals annually, and the majority of these injuries (~9000) are mild in nature; therefore, recruiting 80 TBI subjects and 80 healthy controls over 3 years is felt to be a feasible goal.

## 7. Resources Available

PROTOCOL TITLE: Transcranial direct current stimulation for treatment of deficits after traumatic brain injury.

### **Facilities/Resources of the UNM Center for Brain Recovery and Repair**

Traumatic brain injuries are a common clinical disorder treated at UNM. Approximately 10,000 New Mexicans seek treatment for a TBI each year. As UNM is the only Level 1 trauma center in the region and is situated in the largest city in the state with a metropolitan catchment area population of 1 million, a large percentage of the TBIs sustained in New Mexico are treated at UNM. The majority of TBIs are mTBI, with approximately 1000 New Mexicans each year hospitalized with TBI and 9000 mild enough to be treated in the outpatient setting. Therefore, we expect that if 1/10 of New Mexicans with mTBIs present to UNM each year, that equates to 900 mTBIs eligible for screening. We plan to screen these patients and recruit approximately 25-30 annually for the study, meaning that we are aiming to enroll 3% of eligible patients, which we believe is feasible.

**Clinical Study Coordinator**—In Year 1, a clinical study coordinator will be hired to support junior principal investigators' research projects. The study coordinator will be responsible for the coordination and administration of clinical studies under the direction of the Core co-directors. The clinical study coordinator will help develop, implement, and coordinate research and administrative procedures for the successful management of clinical studies; be responsible for scheduling neuropsychological assessments, neuroimaging appointments, and treatment appointments; and will also be responsible for scheduling regular Core group meetings.

PROTOCOL TITLE: Transcranial direct current stimulation for treatment of deficits after traumatic brain injury.

**Research Technician**—In year 1, two technicians will be hired to assist in the junior PI's projects. We will assign one research technician to each of the initial junior PI projects. Their effort will be dedicated to assist in recruitment/screening, neuropsychological assessment administration, scoring and summary report preparation, scheduling of treatments and neuroimaging procedures, as well as data entry of collected data. Research technicians will be made available to assist with other future junior PI projects and pilot projects.

Technicians, research coordinators, and the investigators will undergo standard training in human research standards, ethics, conflict of interest, and also participate in weekly research group meetings regarding the specific protocol being studied, methodological and analytical issues, and subject recruitment, participation, and safety.

**Transcranial Direct Current Stimulation (tDCS)**—A tDCS system (neuroConn: DC-Stimulator PLUS) will be purchased in Year 1, with a second added in Year 2. These are CE-certified medical devices for conducting non-invasive transcranial direct current stimulation (tDCS), alternating (tACS) or random noise (tRNS) current stimulation on subjects. Transcranial stimulation using weak electric currents over a period of several minutes is demonstrated to modify neuronal excitability and circuit function and can serve to provide long-lasting promotion of brain recovery and repair.

**Neuropsychological Assessment Measures**. The Core will establish a library of advanced neuropsychological tools, applicable to assessment of different aspects of recovery and repair following stroke or TBI. The library will be useful for subjects of different ages and severity of injury. This library will include novel, computer-based neuropsychological measures as well as traditional neuropsychological measures long utilized in neuropsychological research projects and recommended for specific clinical populations (e.g., TBI NINDS Common Data Elements). The Core will also develop and maintain an instrument bank of health-outcome measures, including state-of-the-art, computer-administered measures.

1) *National Institutes of Health Executive Abilities: Measures and Instruments for Neurobehavioral Evaluation and Research (EXAMINER)*. EXAMINER is battery of reliable and valid tests of executive function developed under the auspices of the NINDS for clinical investigations and is adaptable across a wide range of ages and disorders ([www.examiner.ucsf.edu](http://www.examiner.ucsf.edu)).

2) *NIH Toolbox: Assessment of Neurological and Behavioral Function*. The NIH Toolbox is a state-of-the-art set of standardized instruments developed by NIH to enhance data collection and advance and accelerate the pace of discovery in neuroscience research. The NIH Toolbox is a recently developed set of brief, computerized measures of key neuropsychological functions appropriate for use throughout the lifespan (i.e., 3+ years old) and across diverse study designs and settings.

3) *Patient Reported Outcomes Measurement Information System (PROMIS®)*. The PROMIS® is a system of highly reliable, precise measures of patient-reported (both child and adult) health status for physical, mental, and social well-being and can be useful in measuring effectiveness of treatment in clinical intervention studies.

**Data and sample collection**. The Core will provide expert neuropsychological and electrophysiological assessment technical support. This will include providing testing rooms, neuropsychological tests and supplies, laptop computers, electroencephalography, and neuropsychology technicians/ psychometricians, as well as data entry and storage. Core staff will assist investigators with scheduling of assessments, neuroimaging, and treatment appointments. The Core will provide space for interventions being studied as part of research projects. Neuropsychological assessment batteries will be administered by Core psychometricians under the supervision of the Core co-directors. Neuropsychological test data will be scored by the psychometricians, with scoring reviewed for accuracy by the supervisors. A neuropsychological test summary prepared by technicians and reviewed by the supervisors will be provided to investigators,

PROTOCOL TITLE: Transcranial direct current stimulation for treatment of deficits after traumatic brain injury.

participants, and referral sources if indicated. If requested, Core co-directors will also provide feedback to participants regarding neuropsychological assessment results. Participant hardcopy data will be stored in locked file cabinets in locked rooms within a locked, security-patrolled building. For analysis, participant data will be entered and stored in REDCap, a web-based electronic data capture program that is secure and HIPAA compliant available through the UNM CTSC Biomedical Informatics (<http://hsc.unm.edu/research/ctsc/BMI/REDCap.shtml>). Neuropsychological data will be entered by psychometrists into study databases with accuracy verified by double using UNM Health Sciences Center Library Services to create a data management plan to manage and provide access of research data collected in line with current NIH policies.

3T MRI is housed immediately proximal to the neuropsychological testing rooms, as part of the MIND Research Network (MRN) advanced biomedical imaging core. The imaging facilities have private changing rooms with lockers for personal items.

Should patients require any medical or psychological care as a consequence of participation in research, UNM Health Sciences Center is located immediately proximal to the MIND Research Network and can provide basic to advanced care 24 hours a day, 7 days a week.

